1.2.2 Vaccines

The first step in making a vaccine for tumor immunotherapy is to choose the target antigen. PSA is expressed essentially only in prostatic epithelial cells (normal and malignant), and the prostate gland is nonessential. Therefore, PSA is a valid target for immunotherapy. The fact that PSA is secreted and not membrane bound limits the use of PSA as a target for humoral immunity, but not the use of PSA as a target of specific cellular immune system attack. Cells, including tumor cells, present endogenously expressed proteins on their surface in the form of peptide MHC complexes. Cytotoxic T lymphocytes (CTLs) recognize and are activated by specific peptides in the context of the appropriate MHC class I molecule on antigen-presenting cells (APCs). This activation can in turn lead to killing of tumor targets by the peptide-specific CTLs. CTL activation as well as tumor recognition and killing are thus dependent on the MHC class I molecule. One allele of MHC class I molecule, HLA-A2, is present in about 50% of the population in the U.S. and several HLA-A2 restricted peptides from PSA have previously been identified.((11);(12))

Ability to Generate PSA-Specific T cells In-Vitro

The use of PSA as a target to elicit tumor-specific T-cell mediated lysis has been validated *in vitro*. Correale et al. demonstrated *in vitro* killing of a PSA-peptide-pulsed HLA-A2+ human cell line by a PSA-specific human CTL cell line, and lysis was blocked by an antibody directed against MHC class I molecules.((13))

It has also been shown that PSA-specific CTLs could be generated that lyse PSA-expressing prostate cancer cells.((11)-(13)) By stimulating normal HLA-A2 donor peripheral blood mononuclear cells (PBMCs) with HLA-A2-restricted PSA peptides in the presence of IL-2, CTL lines were generated that specifically killed PSA expressing HLA-A2+ prostate cell lines, HLA-A2+ cell lines pulsed with PSA peptide and HLA-A2 cells infected with rV-PSA.((12))

Peptide vs. Vector Encoded Tumor-Associated Antigen

An advantage of recombinant poxvirus in developing cancer vaccines is the demonstration that recombinant proteins derived from genes inserted and transcribed in viral genomes are more immunogenic than protein in adjuvant.((14)-(16)) A striking example of this was noted by Kass et al., where it was shown that two injections of CEA protein in adjuvant generated little, if any, of an immune response to CEA in a CEA transgenic (CEA-Tg) mouse.((14)) This would be

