5.2.5 Assay for Immunologic Response

In order to evaluate the potency of clinical vaccines, assays that determine an antigen-specific T lymphocyte response to vaccines have been employed. The ELISPOT assay for IFN production (see **APPENDIX E**) has shown correlation with the results of the CTL assay.(55, 56) The CTL assay has been used successfully in numerous vaccine trials. The ability to detect single cells that produce interferon gamma has led to specificities of 80-95%. Schmittel et al. have shown that the ELISPOT has very good reproducibility both when the same sample is tested at two time points and when an individual is tested at different time points.(57) We have also seen minimal variation in

the flu-specific ELISPOT in patients when tested at time points about 84 days apart.(58)

The primary immunologic endpoint for evaluating the immune response will be the frequency of interferon gamma-releasing T cells specific to PSA-3A, a HLA-A2 restricted epitope of PSA, as measured by the ELISPOT assay. Only the patients who are HLA-A2 positive will undergo ELISPOT analysis. It is planned that all patients will undergo exploratory analysis of the ability to detect CD4 positive responses using a whole protein PSA assay.

In all patients undergoing apheresis, 5×10^8 to 2×10^9 mononuclear cells will be obtained by a single-access (single venipuncture) “four-pass” mononuclear cell procedure on the Haemonetics V-50 instrument, during which 2.0 liters of whole blood would be processed at a flow rate of about 70-80 ml/min. The total duration of the procedure is 90 min to 2 hours. Patients will be required to have a minimum HCT of 28% and a platelet count of at least 75,000 to undergo a Haemonetics procedure. Apheresis will be requested for immunologic testing in patients receiving vaccine at baseline and around weeks 12, 24, and 36(see section 3.4.6).

Anti-PSA antibodies will be measured prior to and following vaccinations using an ELISA assay as previously described ((17)). In addition, tests for anti-vaccinia antibody, anti-fowlpox antibody, anti-GM-CSF antibody, anti-B7.1 antibody, anti-ICAM-1 antibody and anti-LFA-3 antibody will be run in selected patients as previously described. ((35))

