5.4 Statistical Considerations

The primary objective of this randomized trial is to determine if use of a combination of vaccine plus flutamide may be associated with a trend toward improvement in time to treatment failure in patients with stage D0.5 prostate cancer compared to that which would occur with flutamide alone.

Secondary objectives are 1) determining preliminary evidence of any patterns of immunologic effects which differ by treatment including the immunologic effects of flutamide withdrawal on patients continuing on vaccine following a rising PSA on flutamide, 2) estimating toxicity noted on the arms and comparing the results, 3) evaluating, in a preliminary fashion, the effect of vaccine on development of metastatic disease after PSA progression, and 4) evaluating PSA responses and immune responses in patients who have had flutamide stopped at the time of PSA progression and either continue vaccine (Arm B) or have vaccine initiated (arm A) at time of flutamide discontinuation

The trial will be conducted as a randomized pilot trial with two arms as follows:

Arm A: flutamide

Arm B: flutamide + vaccine

Patients will be stratified based on a projected PSA doubling time (PSADT) of > 10 months vs. ≤ 10 months using the last 2 PSA values 1 month apart prior to enrollment on study.

$$\text{PSADT} = \frac{\log(2) \times t}{\log(\text{final PSA}) - \log(\text{initial PSA})}$$

t=time from initial to final PSA determination

$$\log(2) = 0.301$$

Time to treatment failure (TTF) will be the primary endpoint of this trial, where a treatment failure would be defined as a rising PSA (Bublely Criteria, JCO, 1999), development of metastatic disease, or removal from treatment due to excessive toxicity. Because PSA will be measured monthly and metastatic disease will be evaluated every 3 months, this will be sufficiently frequent for the primary evaluation to be made using standard actuarial methods (Kaplan-Meier plots with a log-rank p-value determinations).

The previously published trial of Nilutamide in a similarly eligible population of patients (stage

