D0.5 prostate cancer) conducted at the NCI (protocol 00-C-0137) identified a 7.6 month median time to treatment failure, using the definition above. In the current trial, Flutamide will be used instead of Nilutamide because it has a potentially more favorable toxicity profile. The objective will be to determine, in the context of a randomized phase 2.5 trial, if the addition of vaccine to flutamide alone may be associated with an improvement in time to treatment failure.

The study will be randomized in a 1:1 fashion, and will enroll 33 eligible patients on each of the two arms (66 total), in order to have 80% power to detect a difference between a hypothesized median TTF of 7.6 months on flutamide alone and an increase of 6 months, to 13.6 months, with flutamide + vaccine, using a one-tailed 0.1 alpha level test. This calculation was made using nQuery Advisor version 5, assuming 36 months accrual, an additional 12 months of follow-up for the last patient enrolled, and hazards of 0.0912 per month for flutamide alone and 0.0510 for flutamide and vaccine, with a resulting hazard ratio of 1.788.

The ELISPOT assay will be performed in HLA-A2 patients. The log changes in precursor T cell frequency from pre-treatment to that after 3, 6, and 9 months of therapy will be determined and evaluated for statistical significance, both within an arm and between arms. Since this assay will only be available on a subset of patients, the power to detect differences is unknown and may be limited, and the results will be considered secondary, exploratory and possibly biased. The results will be carefully reported with necessary caveats. In addition, since there is no evidence at this time that HLA-A2 patients will have a significantly different time to treatment failure than those with other HLA types, this parameter will not be used to stratify the randomization.

Toxicity evaluations will take place during each cycle of therapy and worst grades of toxicity, by type, will be compared in a secondary analysis between the study arms.

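### The exploratory between-arm ELISPOT comparison takes log change as its variable and specifies no adjustment for baseline T-cell frequency, which costs precision unless baseline and follow-up are highly correlated.

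*Combined protocol and SAP*

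**What the plan says.** Section 5.4 defines the immunologic analysis variable: "The log changes in precursor T cell frequency from pre-treatment to that after 3, 6, and 9 months of therapy will be determined". These changes are to be "evaluated for statistical significance, both within an arm and between arms". No test, model or covariate is named for the between-arm part.

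Section 5.2.5 gives the assay its standing among the immune measures: "The primary immunologic endpoint for evaluating the immune response will be the frequency of interferon gamma-releasing T cells specific to PSA-3A". It also limits who is assayed: "Only the patients who are HLA-A2 positive will undergo ELISPOT analysis". Section 1.2.2 gives the expected share: "One allele of MHC class I molecule, HLA-A2, is present in about 50% of the population in the U.S". Section 3.4.6 restricts research blood to patients enrolled at the NIH and, from amendment P, makes all immunologic studies optional.

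The plan is open about the status of this comparison. Section 5.4 says that "the power to detect differences is unknown and may be limited, and the results will be considered secondary, exploratory and possibly biased" and promises caveats in the report. The same section settles what the trial is about: "Time to treatment failure (TTF) will be the primary endpoint of this trial".

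**The concern.** Taking follow-up minus baseline on the log scale fixes the slope on baseline at 1. If the correlation between the two log frequencies is below 1, the best slope is usually smaller, and the subtraction adds baseline noise to the contrast. A model that estimates the slope removes that noise with a value already collected for every patient who contributes a change.

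At stake is the precision of a small comparison whose power the plan already calls limited. In a given data set, a chance difference in baseline frequency between arms also moves the change-score estimate away from the true effect, in a direction that can be predicted from the imbalance. HLA type is not a stratification factor, so nothing in the design specifically protects balance within the assayed subset.

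**Working it through.** **The plan's own figure.** The documents give no sample size, SD, effect or power for ELISPOT. The only size to start from is the one for time to treatment failure after amendment F: 31 per arm, 80% power, one-tailed alpha 0.1, medians of 10.0 and 18.0 months, 60 months of accrual plus 24 of follow-up.

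- Hazards: ln 2 / 10 = 0.0693 and ln 2 / 18 = 0.0385, ratio 1.80.
- Freedman events: (2.80/0.80)² × (1.2816 + 0.8416)² = 12.25 × 4.508 = 55.2, so 56.
- Event probabilities are 0.955 and 0.845 (mean 0.900). 56 / 0.900 / 2 = 31.1 per arm, and power at 31 per arm is 80.3%.

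The stated size reproduces.

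**Size of the assayed subset.** 50% of 31 is 15.5 per arm (5th to 95th percentile 11 to 20). The NIH share is not given. At an assumed 75% or 50% it falls to 11.6 or 7.8 per arm, before optional testing. I use 15 as an upper case and 8 as a low one.

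**Assumptions.** Equal SD (sigma) of log frequency at baseline and follow-up, correlation rho, two-sided alpha 0.05. None of these is in the documents.

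**Formulas, n per arm.**
- Change score: variance per patient 2(1 - rho), in sigma² units; SE = sqrt(2(1 - rho) × 2/n); 2n - 2 df.
- Baseline-adjusted: variance per patient 1 - rho²; SE = sqrt((1 - rho²) × 2/n × (1 + 1/(2n - 4))); 2n - 3 df. The last factor is the average price of estimating the slope.
- Variance ratio before that price: (1 + rho)/2.
- Shift of the change score given a baseline imbalance D: (1 - rho) × D, with opposite sign to D. The SE of D is sqrt(2/n), which is 0.365 sigma at n = 15.

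**Worked case, rho = 0.5, n = 15.** Change-score SE = sqrt(1 × 2/15) = 0.365. Power of 80% at 28 df needs a noncentrality of 2.90, so the effect is 2.90 × 0.365 = 1.06 sigma. Adjusted SE = sqrt(0.75 × 2/15 × 27/26) = 0.322. Noncentrality = 1.06/0.322 = 3.29 at 27 df, and power = 88.7%. A 1-SE imbalance shifts the change score by 0.5 × 0.365 = 0.18 sigma, half its own SE.

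| rho | variance ratio | adjusted power, n = 15 | adjusted power, n = 8 | shift at 1-SE imbalance, n = 15 |
|---|---|---|---|---|
| 0.3 | 0.65 | 92.6% | 91.2% | 0.26 sigma |
| 0.5 | 0.75 | 88.7% | 87.0% | 0.18 sigma |
| 0.7 | 0.85 | 84.6% | 82.7% | 0.11 sigma |
| 0.9 | 0.95 | 80.4% | 78.4% | 0.04 sigma |

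In every row the effect is set so that the change score has 80% power.

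**Simulation, n = 15, true effect 1.0 sigma, 20,000 runs.** Over all randomizations the change score averages 0.99 to 1.00. Given an imbalance of +1 SE it averages 0.75, 0.82, 0.89 and 0.96 at the four values of rho, while the adjusted estimate stays at about 1.00.

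**Unequal SDs.** Suppose vaccine response widens the Arm B follow-up SD to 1.5 times baseline, with rho 0.5 in both arms. Change-score variances are 1.00 and 1.75, sum 2.75. With a common slope of (0.50 + 0.75)/2 = 0.625, the residual variances are 0.766 and 1.703, sum 2.469. The saving is 1 - 2.469/2.75 = 10%, against 25% with equal SDs.

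**The case against.** **The plan is silent rather than wrong.** A reader might infer that the comparison will be made without adjustment. The text does not say so: it names a variable and no method. Regressing log change on arm and baseline gives the same arm effect as modelling follow-up, so a change outcome does not exclude adjustment. This stands. The supportable statement is that adjustment is not specified.

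**There is no bias in the usual sense.** A reader might infer that chance imbalance biases the comparison. Randomization rules that out on average, and the unadjusted test keeps its alpha. The conditional shift and the lost precision are also one defect: 2(1 - rho) - (1 - rho²) = (1 - rho)², which is the variance contributed by baseline differences. This stands too.

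**Nothing confirmatory rests on the result.** A reader might take the immunologic endpoint's label as primary to mean that a main trial conclusion is exposed. Section 5.4 calls the results secondary and exploratory, and section 3.4.6 makes the assays optional. That limits the importance of the point. It does not answer it, because a caveat recovers no precision.

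**Rho may be high.** Section 5.2.5 reports good ELISPOT reproducibility and little variation in flu-specific results about 84 days apart. That points toward the end of the range where the gain is small. It does not settle rho for a PSA-specific response that the vaccine is meant to change.

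**Other threats are larger.** Crossover of Arm A to vaccine after 3 months (section 3.1) and selective sampling matter more for this comparison, and a covariate repairs neither. This is correct, and it is why the proposal centres on month 3.

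**Conclusion.** The point holds as a minor, nearly free improvement to an exploratory analysis. Section 5.4 makes log change the between-arm ELISPOT variable and specifies no baseline adjustment. With at most about 15 per arm, adjustment would raise a change-score power of 80% by about 13, 9 and 5 points at rho 0.3, 0.5 and 0.7, and by under 1 point at 0.9. With 8 per arm the gains are about 11, 7 and 3 points, and at rho 0.9 there is a loss of about 2 points. An observed 1-SE baseline imbalance shifts the change-score estimate by 0.18 SD at rho 0.5 and 15 per arm.

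These sizes rest on an assumed rho, equal SDs and two-sided alpha 0.05. They shrink if vaccine response widens the follow-up SD in Arm B. The primary comparison of time to treatment failure is not affected.

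**What to change.** In section 5.4, state that the between-arm ELISPOT comparison at month 3 uses a linear model of log PSA-specific T-cell frequency on arm and baseline log frequency, reported as an adjusted difference (or ratio, after back-transformation) with a 95% CI. Keep the within-arm log changes as descriptive summaries.

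The cost is one sentence and one degree of freedom. No further samples, assays or patients are needed. With very few patients and rho near 0.9, that degree of freedom can slightly outweigh the gain. Comparisons at months 6 and 9 should keep their caveats, because the model does not deal with crossover after month 3 or with selection of the patients who are still assayed.

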Early stopping Rule- Should 2 patients in the first 10 patients enrolled on both arms of the trial exhibit a grade 4 toxicity of any type, regardless of the number of patients enrolled (from 2 to 10), then the trial will be temporarily closed to accrual to reevaluate the use of the agents in this combination. The exact upper 90% confidence bound about 2/10 is 45%, while that about 1/10 is 34%. Thus, while 1/10 is marginally consistent with one third of the patients having toxicity, 2/10 is consistent with more than this amount; thus 2 patients with toxicity early in the study are more than would be tolerated in a phase II study of this type.

Those patients who experience a PSA progression while on their initial, randomized therapy will stop flutamide treatment when this is determined. If they were randomized to receive vaccine + flutamide, they will begin to receive vaccine (alone), and if randomized to flutamide alone, they will start vaccine alone instead. The time to development of metastatic disease from the date of discontinuation of flutamide will be evaluated as a secondary endpoint for each arm, using Kaplan-Meier curves. Descriptive analyses of the pattern of change in PSA over time will also be performed.

It is expected that approximately 20-25 patients per year may be enrolled onto this trial. Thus, in order to obtain 66 evaluable patients, accrual of approximately three years will be expected. In order to allow for a very small number of patients who are inevaluable early after enrollment, the accrual ceiling will be set at 70 patients.

Following amendment F, the study will be continue to be randomized in a 1:1 fashion, and will enroll 31 eligible patients on each of the two arms (62 total), in order to have 80% power to detect a difference between a hypothesized median TTF of 10.0 months on flutamide alone and an increase of 8 months, to 18.0 months, with flutamide + vaccine, using a one-tailed 0.1 alpha level test. This difference assumes that patients enrolled on the study will be equally divided between those who have progressed on combined androgen therapy as well as those who have just begun combined androgen therapy. This calculation was made using nQuery Advisor version 5, assuming 60 months accrual, an additional 24 months of follow-up for the last patient enrolled, and hazards of 0.0693 per month for flutamide alone and 0.0385 for flutamide and vaccine, with a resulting hazard ratio of 1.80.

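### The worst-grade toxicity comparison in 5.4 has no common observation window, exposure adjustment or rule for cycles after flutamide stops, so it may mislead if time to treatment failure differs as hypothesised

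*Combined protocol and SAP*

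**What the plan says.** Secondary objective 2 (sections 1.1.2 and 5.4) is "estimating toxicity noted on the arms and comparing the results". The whole method is one sentence in 5.4: "Toxicity evaluations will take place during each cycle of therapy", and then "worst grades of toxicity, by type, will be compared in a secondary analysis between the study arms".

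Other parts of the protocol determine how long each arm is at risk:

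- **Flutamide** is stopped at PSA progression in both arms (5.4; also 3.1 and 5.2.1.3).
- **Arm A after PSA progression.** Section 5.4 says that "if randomized to flutamide alone, they will start vaccine alone instead". Section 3.1 makes this optional: after 3 months of therapy, with rising PSA and negative scans.
- **Arm B after PSA progression** may continue vaccine without flutamide (3.1).
- **Design hypothesis after amendment F** (5.4): a "hypothesized median TTF of 10.0 months on flutamide alone and an increase of 8 months, to 18.0 months, with flutamide + vaccine", with "hazards of 0.0693 per month for flutamide alone and 0.0385 for flutamide and vaccine, with a resulting hazard ratio of 1.80".

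The same section is more specific for other secondary analyses. ELISPOT changes are read at 3, 6 and 9 months, and time to metastasis has its own start date, the stop of flutamide. Toxicity has neither a time point nor an end date.

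**The concern.** The worst grade a patient ever reaches can only stay the same or rise as observation lengthens. If Arm B stays on flutamide longer because the vaccine delays failure, it has more time to accumulate flutamide-type events, even if the vaccine adds none. The table could then attribute to the vaccine what is due to longer exposure.

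A second, separate problem concerns vaccine-type events. Arm A patients who cross over receive vaccine cycles under the protocol. If those cycles enter the worst grade for Arm A, events caused by vaccine are credited to the flutamide-alone arm, and the difference between arms shrinks.

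The two distortions act on different kinds of toxicity and can be present together. What is at stake is the answer to secondary objective 2. Two analysts following the sentence in 5.4 could also produce different tables from the same data.

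**Working it through.** **Inputs from 5.4 (after amendment F).** Medians 10.0 and 18.0 months; hazards 0.0693 and 0.0385 per month; 31 patients per arm; accrual A = 60 months; further follow-up F = 24 months; one-sided alpha 0.10; power 80%.

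**Assumptions, because the documents give no figures for this analysis.** Risk q of a given toxicity per 28-day cycle, equal in both arms and constant over time; crossover share x; chance v of a vaccine-type event in a vaccinated patient.

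**Step 1: reproduce the plan's own figure.** With exponential failure times (hazard λ) and uniform accrual,

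P(event) = 1 − [exp(−λF) − exp(−λ(A+F))] / (λA).

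This gives 0.955 in Arm A and 0.845 in Arm B, so 31 × (0.955 + 0.845) = 55.8 expected events. Freedman's formula needs 56 events (31.1 per arm), and the power at 31 per arm is 80.3%. The stated 31 per arm is reproduced.

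**Step 2: observed time to failure.** The ratio of hypothesised medians is 18.0/10.0 = 1.80. The mean observed time to failure is P(event)/λ:

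- Arm A: 0.955/0.0693 = 13.8 months
- Arm B: 0.845/0.0385 = 22.0 months (unrounded inputs)
- Ratio: about 1.6

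**Step 3: excess from exposure alone.** Convert q to a monthly rate, μ = −ln(1−q)/(28/30.4375). The chance of at least one event before first failure or end of follow-up is

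μ/(μ+λ) × P(event at rate μ+λ).

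For q = 2%, μ = 0.0220. Arm A: 0.0220/0.0913 × 0.980 = 23.6%. Arm B: 0.0220/0.0605 × 0.937 = 34.0%.

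| q per cycle | Arm A | Arm B | Excess (points, from unrounded values) | First 12 weeks only, A vs B |
|---|---|---|---|---|
| 0.5% | 7.0% | 10.9% | 3.9 | 1.4% vs 1.4% |
| 1% | 13.2% | 19.9% | 6.7 | 2.7% vs 2.8% |
| 2% | 23.6% | 34.0% | 10.5 | 5.4% vs 5.6% |
| 5% | 44.3% | 58.1% | 13.8 | 13.0% vs 13.5% |
| 10% | 62.2% | 74.6% | 12.4 | 24.8% vs 25.8% |

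The last column uses μ/(μ+λ) × [1 − exp(−(μ+λ) × 2.76)], where 84 days/30.4375 = 2.76 months. A common 12-week window removes nearly all of the excess.

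In simulated trials with 31 per arm, a two-sided Fisher test at 0.05 rejected in 6% to 14% of trials for q from 1% to 10%.

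**Step 4: dilution from crossover, if those cycles are counted in Arm A.** Suppose a vaccine-type event has chance v with vaccine and none without, and crossover patients carry the same v. The difference between arms then falls from v to v(1 − x). For v = 40% it is 30, 20 and 10 points at x = 25%, 50% and 75%.

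**The case against.** Several counter-arguments are sound, and they limit the point.

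- **A reader might infer that planned time on treatment is 1.8 times longer in Arm B.** The documents do not say so. The 1.80 is a hypothesised ratio of median times to failure. Treatment can continue after failure in both arms, so the ratio of total treatment time cannot be derived. For observed time to failure the ratio is about 1.6.
- **A reader might infer that crossover cycles will be counted in Arm A.** Section 5.4 does not say so. It labels the arms by their assigned regimens and distinguishes initial randomised therapy from what follows, so counting only assigned treatment is a natural reading. On that reading the dilution vanishes and only the exposure effect remains.
- **A reader might infer that the comparison is certainly biased in both directions.** The exposure effect needs time to failure to differ. With no difference, it is zero.
- **Constant risk tends to overstate the effect for early events.** Section 8.3 places about half of reported hepatic cases in the first 3 months and gynecomastia at 3.5 months on average. Vaccinia is given once, on day 1. Removal for toxicity is also itself a treatment failure, so the formula suits toxicities that do not end treatment.
- **The analysis is secondary and unpowered.** The primary test, the sample size and the early stopping rule are not affected. A worst-grade-ever table is also a legitimate description of total burden.

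What these arguments do not supply is the missing rule. No other section gives a window, an exposure adjustment or a place for cycles after flutamide. Later exposure is not negligible either: the other half of the hepatic cases fall after 3 months, and fowlpox boosts continue every 4 weeks.

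**Conclusion.** The point holds as a gap in the toxicity analysis that can distort the answer to secondary objective 2 in the scenario for which the trial is powered. If time to failure differs as hypothesised, an equal constant risk of 0.5% to 10% per cycle yields a spurious Arm B excess of about 4 to 14 points. That range rests on exponential failure times, the stated accrual and follow-up, and assumed values of q.

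The dilution of vaccine-type differences is conditional on an unstated counting rule and on an unknown crossover share. It should be described as possible, not as planned.

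The main harm is to the estimates of added toxicity; false significance is a lesser risk. This is a cheap improvement and does not threaten the trial's primary conclusion.

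**What to change.** In 5.4, replace the toxicity sentence with a rule that does four things:

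1. Limit the between-arm comparison to randomised treatment, from day 1 to the stop of flutamide and before any crossover vaccine. Define any safety tail identically in both arms.
2. Compare worst grade by type over a common early window, for example the first 3 cycles.
3. For grade 3 or higher, add rates per patient-month, or cumulative incidence, over the randomised period. If cumulative incidence is used, do not treat the stop of flutamide as a competing event: read at late times, that gives the same quantity as step 3 of the working and brings the excess back.
4. Tabulate toxicity after flutamide stops separately for both arms: crossover vaccine in Arm A and vaccine alone in Arm B. The second table matters because ending the comparison at the stop of flutamide would otherwise leave Arm B's vaccine-alone events without a place.

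A worst-grade-ever table can stay as a description. Sections 3.1 and 5.4 should also be reconciled on whether vaccine after PSA progression in Arm A is optional.

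The cost is a few sentences and one or two extra tables. Dated dosing and complication notes (5.1) and adverse events (5.5) are already collected. The early window alone misses late events, which the exposure-adjusted results cover.
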